6.2.5 Sponsor Responsibility for Reporting Adverse Events

All Adverse Events will be reported to regulatory authorities, IRB/IECs and investigators in accordance with all applicable global laws and regulations.

The principal investigator / sponsor must promptly review all information relevant to the safety of the drug obtained or otherwise received from foreign or domestic sources, including information derived from any clinical or epidemiological investigations, animal or in vitro studies, reports in the scientific literature, and unpublished scientific papers, as well as reports from foreign regulatory authorities and reports of foreign commercial marketing experience for drugs that are not marketed in the United States. The study principal investigator / sponsor must notify all participating investigators of potential serious risks, from clinical trials or any other source, as soon as possible.

In addition to completing appropriate patient demographic and suspect medication information, the report should include as applicable the following information that is available at the time of report within the Event Description of the MedWatch 3500 form:

- CTCAE term(s) and grade(s)
- current status of study drug
- all interventions to address the AE (testing and result, treatment and response)
- hospitalization and/or discharge dates
- event relationship to study drug

Follow-up reports:

Additional information may be added to a previously submitted report by adding to the original MedWatch 3500 report and submitting it as follow-up or creating supplemental summary information and submitting it as follow-up with the original MedWatch 3500 form.

7.0 STATISTICAL ANALYSIS PLAN

7.1 Analysis Samples

For both the primary safety and efficacy endpoints, the analysis sample will be eligible patients who have taken at least one dose of pembrolizumab. Patients who are eligible but withdraw prior to taking the first dose will not be included in these analyses and will be replaced, so that, barring early stopping, the analysis sample will be 40 patients who have taken at least one dose of drug.

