1.0 TRIAL DESIGN

1.1 Trial Design

This is a phase II, single-center, single-arm trial to evaluate the efficacy and safety of pembrolizumab in post-remission treatment of patients ≥ 60 years with AML who are not candidates for HCT. Patients must have achieved CR or CRi with induction chemotherapy and have an ECOG performance status of 0-1. Patients can receive no consolidation or up to 4 cycles of consolidation per treating physicians' preference. Patients are eligible if their last dose of chemotherapy was received within 3 months of trial enrollment. Remaining in CR or CRi is required prior to enrollment. The enrollment target for this study is 40 patients evaluable for efficacy. Planned analysis will occur 18 months after the initiation of treatment of the last patient on the trial.

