4.8 Subject Withdrawal/Discontinuation Criteria

Subjects may withdraw consent at any time for any reason or be dropped from the trial at the discretion of the investigator should any untoward effect occur. In addition, a subject may be withdrawn by the treating sub-investigator or the Principal Investigator if enrollment into the trial is inappropriate, the trial plan is violated, or for administrative and/or other safety reasons. Specific details regarding discontinuation or withdrawal are provided in Section 6.1.4 – Other Procedures.

A subject must be discontinued from the trial for any of the following reasons:

- The subject or legal representative (such as a parent or legal guardian) withdraws consent.
- Confirmed pathologic disease progression
- Unacceptable adverse experiences as described in Section 6.2.1.2
- Intercurrent illness that prevents further administration of treatment
- Investigator's decision to withdraw the subject
- The subject has a confirmed positive serum pregnancy test

- Noncompliance with trial treatment or procedure requirements
- The subject is lost to follow-up
- Completed 24 months of treatment with pembrolizumab and required follow-up
- Administrative reasons

The End of Treatment and Follow-up visit procedures are listed in Section 5 (Trial Flow Chart) and Section 6.1.5 (Visit Requirements). After the end of treatment, each subject will be followed for 30 days for adverse event monitoring (serious adverse events will be collected for 90 days after the end of treatment as described in Section 6.2.3.1). Subjects who discontinue for reasons other than progressive disease will have post-treatment follow-up for disease status until disease progression, initiating a non-study cancer treatment, withdrawing consent or becoming lost to follow-up. After documented disease progression each subject will be followed by telephone for overall survival until death, withdrawal of consent, or the end of the study, whichever occurs first.

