4.9 Subject Replacement Strategy

Participants who are not evaluable for efficacy because they have not received at least one dose of drug will not be included in analyses for either efficacy or toxicity and will be replaced. Any participant who receives at least one dose of pembrolizumab will be included in both efficacy and safety analyses, and will not be replaced.

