7.2 Statistical Analysis Plan Summary

7.2.1 Primary Efficacy Objective: *To evaluate the time to relapse (TTR) in patients > 60 years with AML in complete remission undergoing post-remission therapy with pembrolizumab.* The time to relapse function will be estimated by the product-limit (Kaplan-Meier) method, with an appropriate 80% confidence interval. Death is considered a censoring event in determining TTR.

The median TTR will also be estimated, along with an appropriate confidence interval. Assuming an exponential time to failure distribution, 26% two-year TTR under the standard induction therapy is associated with a median of 12.3 months. The null hypothesis that the treatment with pembrolizumab offers no increase in TTR will be tested by determining if 12.3 months is within an 80% confidence interval around the median, a one-sided $\alpha=0.10$ test. The sensitivity of the treatment of death as a censoring event will be assessed by repeating the above analysis on relapse-free survival, where death and relapse are both considered events. Patients who drop out of the study will be treated as censored at the last observation time.

Potential prognostic factors for TTR in this population will also be explored. These include the use of consolidation therapy (0 vs 1-4), cytogenetic risk category (high-risk, intermediate risk, or low risk), FLT3 status (FLT3-ITD mutation present or absent), NPM1 status (NPM1 mutation present or absent), age >70 years, minimal residual disease, and ECOG performance status. The survival distributions for TTR will be computed using the Kaplan-Meier method and the log-rank test used to test for statistical differences in the distributions for the aforementioned exposure groups. Multivariate analysis using Cox regression will then be used to adjust for all significant covariates. Patients who drop out of the study will be treated as censored at the last observation time. Patients with missing covariate data will be excluded from this exploratory analysis.

7.2.2 Primary Safety Objective: *To evaluate the safety and tolerability of pembrolizumab in patients > 60 years with AML.* The NCI CTCAE type and grade of adverse events and their association with treatment will be tabulated. Section 8.3 contains a stopping rule for excess toxicity.

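### Sections 7.1 and 4.9 define the primary analysis set differently: 7.1 restricts it to eligible dosed patients, while 4.9 includes every dosed patient

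*Combined protocol and SAP*

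**What the plan says.** Section 7.1 covers both the primary safety and the primary efficacy endpoint: "the analysis sample will be eligible patients who have taken at least one dose of pembrolizumab". Its replacement rule covers one group only: "Patients who are eligible but withdraw prior to taking the first dose will not be included in these analyses and will be replaced". It then concludes that, "barring early stopping, the analysis sample will be 40 patients who have taken at least one dose of drug".

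Section 4.9 sets a different rule: "Any participant who receives at least one dose of pembrolizumab will be included in both efficacy and safety analyses, and will not be replaced". It treats as not evaluable only those who never received a dose.

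Section 1.1 gives the target: "The enrollment target for this study is 40 patients evaluable for efficacy". Section 4.8 allows a subject to be withdrawn "if enrollment into the trial is inappropriate", so the protocol foresees that someone may be enrolled who should not have been.

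The stopping rule in Section 7.3 counts patients and toxicities and sets no eligibility condition.

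**The concern.** The two sections place the same patient differently. A patient who is dosed and later found ineligible is in both analyses under 4.9 and in neither under the literal wording of 7.1.

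This matters most for safety, which is a primary objective. Exposure, not eligibility, puts a patient at risk of drug toxicity, so a primary safety table that leaves out exposed patients is incomplete.

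For TTR the issue is pre-specification. Treatment is open-label, there is one arm, and the median is compared with a fixed 12.3 months, so no control arm would share the effect of a selective exclusion. A filter that can be applied after relapse or toxicity is known should not be left to interpretation.

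**Working it through.** **1. The two rules side by side**

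| Patient | Section 7.1, literal | Section 4.9 |
|---|---|---|
| Eligible, dosed | In both analyses | In both analyses, not replaced |
| Eligible, never dosed | Out, replaced | Out, replaced |
| Found ineligible, dosed | Out; replacement not mentioned | In both analyses, not replaced |

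Only the last row conflicts.

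**2. Is eligibility clear-cut?** Section 1.1 allows anything from no consolidation to 4 cycles, as the treating physician prefers. Section 4.1.1 calls for 2 to 4 cycles and accepts fewer than 2 only where the physician deems the patient intolerant. The list in Section 4.1.2 gives no minimum number of cycles. A patient with 0 or 1 cycle and no recorded intolerance is therefore eligible under Section 1.1 and not under Section 4.1.1. The sections must be reconciled before any eligibility filter has a fixed meaning.

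**3. Size of the set.** Let k be the number of dosed patients found ineligible. With 7.1's filter and 4.9's ban on replacement, n = 40 − k. The documents give no rate. Assuming 2.5% to 10% of 40, k = 1 to 4 and n = 39 to 36. If each dosed patient independently has probability q of being found ineligible, the chance that the set is below 40 is 1 − (1 − q)^40: 33% at q = 1%, 64% at 2.5%, 87% at 5% and 99% at 10%. Under 4.9 alone the set stays at 40.

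**4. Effect on power.** The inputs are a null median of 12.3 months and one-sided α of 0.10 (Section 7.2.1), 80% power at a median of 19.5 months (Section 7.4), 18 to 24 months of accrual (Trial Summary), and analysis 18 months after the last patient starts (Section 1.1).

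- Null median: 24 × ln 2 / (−ln 0.26) = 12.35 months, in line with the plan's 12.3.
- Exponential model: power = Φ(√d × ln(19.5/12.3) − 1.282), where d is the expected number of relapses and ln(19.5/12.3) = 0.461. Power of 80% needs d = ((1.282 + 0.842)/0.461)² ≈ 21.2.
- The plan does not give the confidence interval method or the dropout behind its 80%. With n = 40 and 18-month accrual, this model gives 84.0% with no loss (d = 24.4) and 79.7% with an assumed 15% annual loss (d = 21.0). The stated 80% is therefore reproduced only with assumed loss.

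| Scenario | n = 40 | 39 | 38 | 36 |
|---|---|---|---|---|
| 18-month accrual, no loss | 84.0% | 83.3% | 82.6% | 81.0% |
| 24-month accrual, no loss | 85.5% | 84.9% | 84.1% | 82.6% |
| 18-month accrual, 15% annual loss (assumed) | 79.7% | 78.9% | 78.2% | 76.5% |

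The cost is about 0.6 to 0.8 percentage points per patient.

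**5. Stopping rule, only if the 7.1 set were used for monitoring.** Section 7.4 gives a Beta(2,8) prior and stops when the posterior probability that toxicity exceeds 0.2 is above 0.8. With x toxicities in n patients the posterior is Beta(2 + x, 8 + n − x). This reproduces every boundary in the Section 7.3 table. At 15 patients, 5 toxicities give 0.811 (suspend) and 4 give 0.656 (continue). If one of the five patients with a toxicity is dropped as ineligible, 4 of 14 gives 0.695, below 0.8, and the trial continues.

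**The case against.** Section 7.1 never says outright that dosed patients found ineligible are dropped. The word eligible could mean no more than screened and enrolled, and the paragraph ends with "the analysis sample will be 40 patients who have taken at least one dose of drug", which has no eligibility qualifier. On that reading the two sections agree. This is a fair reading, and the exclusion is an inference from one word. But on that reading the word does no work in the defining sentence, and an analyst who follows the sentence literally would apply the filter. The text needs to settle it.

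A reader might infer three stronger claims. The documents do not support them:

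- *Exposed patients disappear from the safety data.* Sections 6.2 and 6.2.3.1 record and report adverse events from consent with no eligibility limit, and Section 9.5 reviews all toxicities as they occur. Only the primary safety tabulation is at issue.
- *The stopping rule is weakened.* Section 7.3 counts patients without an eligibility condition. The 5/15 and 4/14 comparison needs the unstated assumption that the 7.1 set is used for monitoring. It also takes a case at the boundary, removes a patient who had a toxicity, and looks at 14 patients, where the table has no entry.
- *The trial will be underpowered.* A set below 40 needs both sections' rules together and an assumed ineligibility rate, and the power cost is small.

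Nor do the documents plan a retrospective eligibility review, and eligibility is checked before treatment. Biased exclusion from TTR is therefore a possibility left open, and its size cannot be estimated here. An efficacy set of treated and eligible patients is also a defensible phase II choice. The case for all dosed patients is strongest for safety. For TTR it rests on consistency with 4.9 and on closing a discretionary step.

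**Conclusion.** The inconsistency stands. Sections 7.1 and 4.9 give different primary analysis sets for any patient who is dosed and later found ineligible, and the documents do not say which governs. Followed literally, 7.1 leaves such a patient out of the primary safety tabulation and the TTR analysis. The main harm is to the completeness of the safety table and to pre-specification, made worse by the conflicting consolidation requirement.

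The numerical effect is minor: one patient fewer than 40 for each case, and well under one percentage point of power each under exponential TTR and the accrual and loss assumptions shown. The number of such cases is unknown. The stopping-rule effect is conditional on a use of the 7.1 set that the plan does not state. The point is worth correcting because the correction costs almost nothing and is best made before outcomes are seen.

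**What to change.** - Define the analysis sample in 7.1 as all patients who received at least one dose of pembrolizumab, for both the safety and the primary TTR analyses. This matches 4.9 and makes the stated 40 hold.
- State in 7.3 that the stopping rule counts all dosed patients.
- Report TTR in the eligible-only set as a sensitivity analysis, with eligibility judged against criteria fixed in advance.
- Reconcile Sections 1.1 and 4.1.1 on consolidation, so that the eligible-only set has one meaning.

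The cost is a few sentences of text and one small additional analysis. No change to the sample size is needed.

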7.2 Statistical Analysis Plan Summary

7.2.1 Primary Efficacy Objective: *To evaluate the time to relapse (TTR) in patients > 60 years with AML in complete remission undergoing post-remission therapy with pembrolizumab.* The time to relapse function will be estimated by the product-limit (Kaplan-Meier) method, with an appropriate 80% confidence interval. Death is considered a censoring event in determining TTR.

The median TTR will also be estimated, along with an appropriate confidence interval. Assuming an exponential time to failure distribution, 26% two-year TTR under the standard induction therapy is associated with a median of 12.3 months. The null hypothesis that the treatment with pembrolizumab offers no increase in TTR will be tested by determining if 12.3 months is within an 80% confidence interval around the median, a one-sided $\alpha=0.10$ test. The sensitivity of the treatment of death as a censoring event will be assessed by repeating the above analysis on relapse-free survival, where death and relapse are both considered events. Patients who drop out of the study will be treated as censored at the last observation time.

Potential prognostic factors for TTR in this population will also be explored. These include the use of consolidation therapy (0 vs 1-4), cytogenetic risk category (high-risk, intermediate risk, or low risk), FLT3 status (FLT3-ITD mutation present or absent), NPM1 status (NPM1 mutation present or absent), age >70 years, minimal residual disease, and ECOG performance status. The survival distributions for TTR will be computed using the Kaplan-Meier method and the log-rank test used to test for statistical differences in the distributions for the aforementioned exposure groups. Multivariate analysis using Cox regression will then be used to adjust for all significant covariates. Patients who drop out of the study will be treated as censored at the last observation time. Patients with missing covariate data will be excluded from this exploratory analysis.

7.2.2 Primary Safety Objective: *To evaluate the safety and tolerability of pembrolizumab in patients > 60 years with AML.* The NCI CTCAE type and grade of adverse events and their association with treatment will be tabulated. Section 8.3 contains a stopping rule for excess toxicity.

7.2.3 Secondary Efficacy Objective: *To evaluate overall survival with post-remission pembrolizumab treatment in patients \geq 60 years with AML.* The analysis plan is similar to that of TTR. Assuming an 8% five-year survival rate with induction therapy alone, median overall survival is 17.2 months.

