| 9.3 | Compliance with Trial Registration and Results Posting Requirements | 52 |

| | | |
|------|--|-----|
| 9.4 | Quality Management System..... | 52 |
| 9.5 | Data Management..... | 52 |
| 10.0 | LIST OF REFERENCES..... | 543 |
| 11.0 | APPENDICES..... | 58 |
| 11.1 | ECOG Performance Status..... | 58 |
| 11.2 | Common Terminology Criteria for Adverse Events V4.0 (CTCAE)..... | 58 |

TRIAL SUMMARY

[figure not shown]
| | |
|---------------------------------------|---|
| Title | A Phase II study of Pembrolizumab as Post-remission Treatment of Patients ≥ 60 with AML Who Are Not Transplantation Candidates |
| Short Title | Pembrolizumab as Maintenance Therapy for AML in CR1 |
| Protocol Number | |
| Phase | Phase II |
| Methodology | Open label |
| Study Center(s) | Single-center |
| Primary Objective | To evaluate the time to relapse (TTR) in patients > 60 years with AML in complete remission undergoing post-remission therapy with pembrolizumab. |
| Number of Subjects | 40 subjects |
| Diagnosis and Main Inclusion Criteria | Patients with AML in first complete remission/complete remission with incomplete count recovery who are not unable or unwilling to undergo allogeneic stem cell transplant or who allogeneic stem cell transplant is not indicated. |
| Study Product, Dose, Route, Regimen | Pembrolizumab, intravenous, 200mg, every 3 weeks with dosing adjustments as needed for toxicity |
| Duration of administration | Total duration of pembrolizumab is up to 2 years if patients tolerate the therapy and remain in complete remission |
| Reference therapy | Patients who achieve a complete response to induction chemotherapy followed by chemotherapy consolidation therapy who do not undergo allogeneic transplant are observed. Despite the high relapse rates in this group, there is not therapy that has been proven to be effective to prevent relapse. |
| Statistical Methodology | The relapse function will be estimated by using the Kaplan-Meier method. A 26% two-year TTR under the standard induction therapy is associated with a median of 12.3 months. The null hypothesis that the treatment with pembrolizumab offers no increase in TTR will be tested by determining if 12.3 months is within an 80% confidence interval around the median, a one-sided $\alpha=0.10$ test. |
| Estimated Enrollment Period | 18-24 months |
| Estimated duration of trial | 4 years, but with planned analysis at 18 months after last patient enrolled |

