3.2 Rationale

3.2.1 Rationale for the Trial and Selected Subject Population

Acute myeloid leukemia (AML) is a malignant hematopoietic disorder characterized by the unregulated growth of myeloid precursors (blasts) and associated marked reduction in normal hematopoiesis. It is the most common acute leukemia in adults, with an estimated 18,860 new cases of AML diagnosed per year in the United State and 10,460 deaths. [23] Disease related morbidity and mortality arise from cytopenias, leading to complications such as bleeding and/or infection, as well as end organ damage from the circulating blasts. If left untreated, AML can lead to death within weeks. [24]

The standard treatment for newly diagnosed AML consists primarily of an anthracycline combined with a nucleoside analogue, cytarabine. The goal of remission induction chemotherapy is the rapid restoration of normal bone marrow function. [25] Once a complete remission is attained, relapse invariably occurs without additional consolidation therapy. Consolidation approaches are based on prognosis and age, but may include 1-4 cycles of high dose cytarabine chemotherapy or allogeneic stem cell transplant. While consolidation therapy reduces relapse, up to 50% of younger patients still relapse. [26]

Although standard therapeutic approaches are tailored to younger patients, the median age of diagnosis of acute myelogenous leukemia (AML) is 67 years. [27] Unfortunately, the outcomes for patients older than 60 years are quite poor. Population studies in AML report 5-year survival rates of 3% to 8% compared to up to 50% for younger patients. [28] Intensive induction therapy, as described above, remains the standard of care for those elderly patients who are able to tolerate it, but rates of complete remission (CR) range from 20% to 60% dependent on the number of adverse prognostic conditions present. [29] The 2-year DFS of patients ≥ 60 yrs of age with AML who undergo induction therapy has been consistently at 24-26% in two large studies conducted in 2001 and 2010. [30; 31] Unfortunately, there have been no important advances in induction therapy since then.

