Although patients ≥ 60 years old can obtain a morphologic CR, defined as hematopoietic recovery with $\leq 5\%$ blasts present, relapse still occurs in up to 80% of these patients. [32] These high relapse rates demonstrates that the majority of patients ≥ 60 years old have submicroscopic residual disease (MRD), leading to subsequent relapse. Reduced intensity conditioned (RIC) allogeneic stem cell transplant (HCT) offers a survival benefit when performed after induction chemotherapy for a proportion of patients with high-risk AML. [33; 34; 35] Unfortunately, transplant-related mortality remains high in elderly patients and those with multiple comorbidities, limiting the availability of this consolidation approach for many patients over the age of 60. [35] In a prospective study aimed to offer RIC transplant to all eligible patients with high-risk AML over age 50, only 15% of patients in CR proceeded with allogeneic stem cell transplant. [36] New strategies to prevent relapse in older patients who are not eligible or willing to undergo an allogeneic transplant are desperately needed.

Acute myeloid leukemia (AML) has historically been sensitive to immunotherapy. The graft-versus-leukemia (GVL) effect of allogeneic hematopoietic stem cell transplant (HCT) is a well-established, successful form of immunotherapy. AML is the most common indication for HCT in North America. [37] Donor lymphocyte infusions performed for relapsed AML, which rely solely on the GVL effect, lead to complete remission (CR) rates of 15-29%. [38; 39] The CRs attained through DLI are frequently durable. [40]

Despite the sensitivity of AML to immune attack, the microenvironment in AML is immunosuppressive, facilitating immune tolerance of leukemia cells. In vitro studies have demonstrated that factors secreted by primary AML cells, particularly arginase II, can prevent T-cell activation and proliferation. [41; 42] Tregs are also critical mediators of immunosuppression in AML. [43] Increased Tregs are present in patients with AML at various stages of diagnosis and treatment. Tregs are increased at diagnosis in patients with AML compared to healthy controls [44; 45; 46] and higher frequencies at diagnosis are associated with a poor prognosis. [44; 45] Early recovery from both cytotoxic chemotherapy and

maintenance therapy for AML also led to increased frequencies of functional immunosuppressive Tregs. [47; 48]

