7.4 Justification of Design

The plot presents the power of the hypothesis test of the primary efficacy endpoint against the median TTR after *pembrolizumab* treatment. It is seen that 80% power is achieved (at $\alpha=0.1$ in a one-sided test) if the true median TTR is 19.5 months or greater. The stopping rule is based on a beta-binomial probability model that stops the trial if $PP(P(\text{Toxicity}) > 0.2) > 0.8$, where PP is the posterior probability function for $P(\text{Toxicity})$. The posterior model includes a binomial data model and a Beta(2,8) prior for the $P(\text{Toxicity})$. The plot displays the operating characteristics of the rule as a function of the true (unobserved) probability of toxicity. It is seen that, for instance, if the true probability of toxicity is 0.4, the probability the trial will stop early is 0.5, and the expected number of patients accrued is 28.

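### The 12.3-month null median is a two-year rate converted through an unsupported exponential curve, so the primary test's error rate against the real benchmark depends on curve shape; testing the 24-month rate directly, with matching event definitions, avoids this

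*Combined protocol and SAP*

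**What the plan says.** The historical evidence is in section 3.2.1: "The 2-year DFS of patients ≥ 60 yrs of age with AML who undergo induction therapy has been consistently at 24-26" per cent, from two studies. It is a rate at one time point, and it is disease-free survival.

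Section 7.2.1 converts the upper figure to a median: "Assuming an exponential time to failure distribution, 26% two-year TTR under the standard induction therapy is associated with a median of 12.3 months". The Trial Summary repeats the conversion without naming the exponential: "A 26% two-year TTR under the standard induction therapy is associated with a median of 12.3 months". The null hypothesis of no increase in TTR is then "tested by determining if 12.3 months is within an 80% confidence interval around the median, a one-sided" test at 0.10. The interval is described only in general terms: "The median TTR will also be estimated, along with an appropriate confidence interval". Deaths are censored. A sensitivity analysis repeats the same procedure with death and relapse both as events.

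Section 7.4 adds the operating characteristics: "It is seen that 80% power is achieved" at one-sided 0.1 "if the true median TTR is 19.5 months or greater". The sample is 40 treated patients (7.1), and the analysis takes place 18 months after the last patient starts treatment (1.1).

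**The concern.** The null is meant to represent what happens without pembrolizumab. What is known about that is a probability at 24 months. What is tested is a median near 12 months. The exponential is the only link between the two, and the document gives no reason to expect a constant hazard after remission. The planned sensitivity analysis changes how deaths are counted but not the curve shape.

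If the historical curve falls faster early and then flattens, its true median is below 12.3 and the test is too strict, so a useful drug may be missed. If the hazard rises over time, the true median is above 12.3 and an inactive drug passes too often. The trial has a single arm, so no control group would reveal either error.

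**Working it through.** **Inputs.** 26% at 24 months, 12.3 months, 80% interval (7.2.1); 19.5 months (7.4); N = 40 (7.1); accrual of 18-24 months (Trial Summary); analysis 18 months after the last start (1.1). Assumed: uniform accrual and no dropout.

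**The plan's figures.** The exponential median is 24 × ln 2 / (−ln 0.26) = 24 × 0.6931 / 1.3471 = 12.35, so 12.3 reproduces. Everyone has at least 18 months of potential follow-up. With no dropout or death, the Kaplan-Meier estimate at 12.3 months is therefore a simple proportion of 40. The lower 80% limit for the median exceeds 12.3 when that proportion's lower limit exceeds 0.5:

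- Linear interval: 24/40 gives a limit of 0.501, so the rule is at least 24.
- Log-log interval: 24/40 gives 0.494 and 25/40 gives 0.519, so the rule is at least 25.

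For a true median of exactly 12.3, the exact error is 0.134 (linear) or 0.077 (log-log). At an exponential median of 19.5, S(12.3) = 0.646 and power is 0.782 or 0.675. The 80% in 7.4 is thus roughly met with a linear interval and not with log-log.

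**Other shapes through the same 26%.**

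- Plateau: S(t) = c + (1 − c)exp(−kt). For c = 0.20, exp(−24k) = 0.06/0.80 = 0.075 and k = 0.1079. The median is −ln(0.30/0.80)/k = 9.1 months.
- Weibull: S(t) = 0.26^((t/24)^a), with median 24 × (0.6931/1.3471)^(1/a). For a = 1.3 this is 14.4 months.

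The target effect is a hazard ratio of 12.3/19.5 = 0.63 in every row. Size is P(Bin(40, S(12.3)) ≥ r), and power uses S(12.3)^0.63.

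| Null shape, S(24) = 0.26 | Median | S(12.3) | Size/power, log-log (r = 25) | Size/power, linear (r = 24) |
|---|---|---|---|---|
| Exponential | 12.35 | 0.501 | 0.080 / 0.68 | 0.138 / 0.79 |
| Plateau 10% | 11.3 | 0.471 | 0.037 / 0.56 | 0.071 / 0.68 |
| Plateau 20% | 9.1 | 0.412 | 0.005 / 0.30 | 0.013 / 0.42 |
| Weibull 0.7 | 9.3 | 0.430 | 0.010 / 0.38 | 0.023 / 0.50 |
| Weibull 1.3 | 14.4 | 0.568 | 0.289 / 0.89 | 0.407 / 0.94 |

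**Testing the 24-month probability instead.** Reject if the lower limit of the two-sided 80% Kaplan-Meier interval at 24 months exceeds 0.26. The alternative is 0.26^0.63 = 0.43. Simulation (6,000 trials per cell, accrual 18 or 24 months) gives size 0.08-0.09 and power 0.78-0.81 in all five shapes, with either interval. Under the null, about 7 to 8 of 40 patients remain at risk at 24 months. Patients with less than 24 months of potential follow-up make up 6/24 = 25% to 6/18 = 33%. Random dropout of 1% a month lowers log-log power to about 0.75.

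**Event definition.** Suppose 20% of failures are deaths in remission (illustrative), with constant hazards. The death-censored 24-month probability is then 0.26^0.8 = 0.34 with no drug effect. Testing death-censored TTR against 26% would reject 36-40% of the time, so the landmark test alone is not enough.

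**The case against.** - **Conflict with the relapse ceiling.** A reader might infer that the exponential contradicts section 3.2.1, where "relapse still occurs in up to 80% of these patients", because the curve reaches 97% failed at five years. The document does not support that. The 80% has no time horizon and a different source from the 26%. The exponential does not pass 80% until 28.7 months. The 26% also counts deaths, so a curve can fall below 20% event-free while only 80% relapse. Nor does the document establish a plateau.
- **Unknown error rate and power.** A reader might also infer this, but it is too strong. The median interval is non-parametric. Against a true median of 12.3 its error can be calculated, and the stated power roughly reproduces with a linear interval. What is unsupported is that 12.3 represents the historical experience.
- **The inflated-error case is invented.** Nothing in the document points to Weibull 1.3, and the plateau and Weibull 0.7 cases make the test conservative. This stands: the table shows sensitivity and does not predict a direction.
- **The power comparison favours the landmark.** Largely true. Fixing the hazard ratio fixes the 24-month rate at 43% in every shape. If the true median is held at 19.5 months instead, the current rule's power under the 20% plateau is 0.45 (log-log) or 0.58 (linear), not 0.30 or 0.42. Under Weibull 1.3 the landmark's power is about 0.70, below the median rule's 0.83 (log-log), whose size is inflated there. The stable size does not depend on this choice.
- **Partly handled already.** The exponential is stated openly, and the whole Kaplan-Meier curve with an 80% interval is planned. The 24-month estimate will exist, but it does not decide the trial.

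**Conclusion.** The point holds in this form: the threshold of the primary test rests on a shape assumption that the document does not support, and the benchmark as reported does not need it. Across the illustrative shapes, the median rule's error against a 26% two-year rate runs from 0.5% to 29% with a log-log interval and from 1% to 41% with a linear one. The 24-month test stays at 8-9%. Even under the plan's own exponential it does at least as well overall: size 0.09 and power 0.79-0.81, against 0.08 and 0.68 (log-log) or 0.14 and 0.79 (linear).

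This rests on uniform accrual, no dropout unless stated, and shapes chosen for illustration. The direction of the error in this trial is not known. The landmark test is properly calibrated only if its endpoint and its benchmark treat deaths in the same way.

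**What to change.** In section 7.2.1 and the Trial Summary:

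- Base the primary decision on the Kaplan-Meier probability at 24 months. Reject the null if the lower limit of a named two-sided 80% interval (for example log-log) exceeds 26%.
- Because the 26% is disease-free survival, apply the rule to relapse-free survival, with death and relapse as events. Alternatively, keep death-censored TTR and replace the 26% with a benchmark that also censors deaths.
- Keep the median and its interval as descriptive results.
- State how relapses found in the two-year marrow window (±4 weeks, section 6.1.2.6) are counted, since the landmark falls inside it.

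In section 7.4, restate power as about 80% for a true 24-month rate of about 43%, and say that this rate is a design target.

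The cost is SAP wording and a recalculated power statement, with no added patients or visits. The downsides are the small number still at risk at 24 months and some loss of power with early dropout.
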